1.0 OBJECTIVES

1.1 Primary Objectives

- 1.1.1 To assess the efficacy of erlotinib in patients with refractory or relapsed AML.
- 1.1.2 To determine the safety and tolerability of erlotinib in this patient population.

1.2 Secondary Objectives

- 1.2.1 To investigate inhibitory effect of this drug on SYK and its down-stream targets such as JNK, MAPK and Erk.
- 1.2.2 To evaluate its role in Jak/STAT pathway and to investigate erlotinib-mediated cell death and/or differentiation.
- 1.2.3 To quantitate concentrations of plasma erlotinib.

2.0 BACKGROUND

Acute myeloid leukemia (AML) is a malignancy of immature granulocytes or monocytes. Malignancy is characterized by accumulation of leukemic blastocytes and blockade of normal bone marrow production resulting in thrombocytopenia, anemia, and neutropenia. In the U.S., approximately 11,930 new cases of AML are expected to be diagnosed in 2006, with an estimated 9,040 deaths occurring in the same time period. Almost all newly diagnosed cases, as well as deaths, will be in adults.¹ Standard treatment for AML includes systemic combination chemotherapy to control bone marrow and systemic disease. Treatment is generally divided into an induction phase, to attain remission, and a maintenance phase. Approximately 60% to 70% of adults with AML can be expected to attain complete remission status following appropriate induction therapy. Remission rates in adult AML are inversely related to age, with an expected remission rate of >65% for those younger than 60 years. Increased morbidity and mortality during induction appear to be directly related to age.²

Standard therapy for hematologic malignancies, particularly acute leukemias, has changed little over the past 20-30 years. This is in part due to the lack of understanding, until recently, of the biology of the disease which has led to little change in the management of these patients. The treatment has been based on combination therapy with standard chemotherapy agents. In acute myeloid leukemia, typically with an anthracycline and cytarabine, and in acute lymphoblastic leukemia with multi-agent therapy. Recent advances in the discovery of important molecular abnormalities has led to the development of new agents that are likely to change the outcome of patients and the standard approach to the treatment of these patients. Some examples are already in clinical practice (eg, the use of all-trans retinoic acid-based therapy for patient with PML/RAR α rearrangements) and others are in development with great possibilities of

being approved in the near future (eg, FLT3 inhibitors, alone or in combination with chemotherapy). However, there is urgent need for identification of new therapeutic targets and agents that may be used for these patients.

2.1 Erlotinib

Erlotinib, a potent, selective, and reversible inhibitor of tyrosine kinase activity associated with the HER1/EGFR, has demonstrated tumor growth inhibition both in vitro and in vivo. Erlotinib was designed to target the signaling pathway that mediates the effects of EGFR activation on cell proliferation.

Erlotinib 150 mg orally once daily for the treatment of patients with locally advanced or metastatic NSCLC after failure of at least 1 prior chemotherapy regimen was approved in the US on 18 November 2004 and in the EU on 19 September 2005, based on data from the randomized, placebo-controlled Study BR.21. This trial demonstrated a statistically significant and clinically meaningful survival benefit, as well as delayed time to deterioration of lung cancer symptoms, in patients who received erlotinib. This indication has now been approved in multiple countries worldwide.

Also, erlotinib 150 mg daily has been approved by European regulatory authorities for use as maintenance therapy in patients with advanced or recurrent NSCLC who had stable disease following 4 cycles of a platinum-based doublet chemotherapy. In the US, erlotinib 150 mg daily is approved for use as maintenance therapy in patients with advanced or recurrent NSCLC who have not progressed after 4 cycles of first-line platinum-based doublet chemotherapy. These indications are based on results from the SATURN study, a multicenter, double-blind, randomized phase 3 study that demonstrated statistically significant and clinically relevant improvement in progression-free survival (PFS) and overall survival (OS).

Two additional phase 3 clinical trials of erlotinib have been completed in NSCLC patients:

- First-line treatment of NSCLC, concurrently administered in combination with carboplatin/paclitaxel (Study OSI2298g); this trial showed no benefit of the addition of erlotinib to first-line chemotherapy for NSCLC.
- First-line treatment of NSCLC, concurrently administered in combination with cisplatin/gemcitabine (Study BO16411); this trial showed no benefit of the addition of erlotinib to first-line chemotherapy for NSCLC.

2.1.1 Adverse Events

As of 15 November 2010, more than 33,000 healthy subjects and cancer patients have participated in company-sponsored and investigator-

sponsored studies; more than 22,000 of these subjects or patients are estimated to have received erlotinib.

The Global Drug Safety Database contains approximately 9243 unique clinical study serious adverse events assessed as related to erlotinib in a total of 5846 patients (see table below).

MeDRA System Organ Class Preferred Terms	Fatal Events	Total Events
Infections and infestations		
Pneumonia, pneumonia primary atypical, lung infections, upper/lower respiratory tract infection, bronchitis	56	230
Cellulitis, infection, abscess, localized infection, folliculitis, skin infection	8	137
Sepsis, staphylococcal sepsis, bacteremia, sepsis syndrome	26	64
Neutropenic sepsis	2	5
Pharyngitis, herpangina, tonsillitis	-	4
Cellulitis orbital	-	1
Endometritis	-	1
Blood and lymphatic system disorder		
Neutropenia, leucopenia, agranulocytosis	5	104
Febrile neutropenia	-	69
Anemia	3	158
Thrombocytopenia	4	73
Pancytopenia, bone marrow failure	2	10
Coagulopathy, disseminated intravascular coagulation, hemorrhagic diathesis	8	15
Hemolytic uremic syndrome, TTP	-	3
Leukocytosis	-	1
Metabolism and nutrition disorders		
Dehydration	7	294
Anorexia, failure to thrive, malnutrition, cachexia	1	243
Hypokalemia	-	34
Other electrolyte imbalance (Na+, Ca++, Mg++, phosphate)	-	86
Hyperglycemia, hypoglycemia	1	18
Psychiatric disorders		
Confusional state, mental status changes, disorientation	-	37
Anxiety	-	2
Depression	-	4
Nervous system disorders		
CVA, cerebral infarction, hemorrhagic stroke, TIA, hemiparesis, cerebral artery embolism	29	93
Headache	1	19
Neuropathy peripheral, paraesthesia	-	14

Lethargy, depressed consciousness	1	19
Aphasia	-	4
Coordination abnormal	-	1
Dizziness, vertigo	-	34
Syncope	-	17
Myasthenia gravis	-	1
Eye disorders		
Keratitis, keratoconjunctivitis sicca/dry eye, punctuate keratitis	-	12
Conjunctivitis	-	14
Ectropion	-	1
Uveitis, iridocyclitis	-	5
Vision blurred, visual disturbance, blindness	1	14
Corneal erosion/ulceration/perforation	-	6
Cardiac disorders		
Acute myocardial infarction, acute coronary syndrome, angina	15	57
Cardiac arrest, cardio-respiratory arrest	15	17
Cardiovascular disorder	2	2
Atrial fibrillation/supraventricular tachycardia/tachycardia	-	27
Cardiac failure acute, cardiac failure congestive, left ventricular failure, left ventricular systolic dysfunction	5	29
Bradycardia	1	4
Vascular disorders		
Deep vein thrombosis, phlebothrombosis, thrombosis, jugular vein thrombosis	-	81
Hypotension, orthostatic hypotension	4	33
Vasculitis, vasculitis necrotizing	-	7
Peripheral embolism, embolism	-	9
Hypertension, hypertensive crisis	-	18
Peripheral ischemia	-	3
Respiratory, thoracic, and mediastinal disorders		
Pneumonitis, interstitial lung disease, bronchiolitis obliterans and organizing pneumonia (BOOP), lung infiltration, alveolitis	198	621
Dyspnea	34	218
Pulmonary embolism	17	107
Respiratory distress, acute respiratory distress syndrome	14	25
Respiratory failure, respiratory arrest	30	37
Anemic hypoxia, hypoxia	3	26
Hemoptysis, pulmonary hemorrhage	18	48
Epistaxis	-	20
Pharyngolaryngeal pain	-	3
Pulmonary fibrosis	1	21
Cough	1	20
Respiratory acidosis	1	1

Gastrointestinal disorders		
Diarrhea	16	873
Vomiting	2	332
Nausea	1	269
Gastrointestinal hemorrhage, melena, hematemesis, rectal bleeding	21	188
Mouth hemorrhage	-	2
Pancreatitis	1	24
Stomatitis, mouth ulceration, glossitis	-	98
Colitis, enterocolitis, cecitis	2	18
Abdominal pain, dyspepsia	2	103
Diarrhea hemorrhagic	-	4
Intestinal ischemia	1	4
Gastric Ulcer/Duodenal Ulcer	1	34
Esophagitis, gastritis	-	33
Intestinal perforation, gastrointestinal perforation, gastrointestinal ulcer perforation, diverticular perforation	14	37
Constipation	-	30
Dysphagia	-	27
Pneumoperitoneum	1	4
Hepatobiliary disorders		
Hyperbilirubinemia	-	51
Cholecystitis	-	8
Jaundice	-	8
Hepatic function abnormal, liver disorder	7	112
Hepatic steatosis	1	2
Hepatitis, hepatic failure, hepatotoxicity	15	31
Skin and subcutaneous tissue disorders		
Rash, dermatitis acneiform, exanthematous pustulosis, dermatitis, exanthema, acne, rash pustular, skin toxicity	-	698
Dermatitis exfoliative	-	31
Dermatitis bullous, blister	1	2
Stevens Johnson syndrome, erythema multiforme, skin necrosis	2	9
Dactylitis	-	2
Pruritus	-	14
Urticaria	-	8
Eczema	-	14
Hyperhidrosis	-	2
Paronychia	-	22
Palmar plantar erythrodysesthesia syndrome	-	14
Alopecia	-	2
Dry skin	-	8

Nail disorder, ingrowing nail, hair growth abnormal	-	8
Musculoskeletal and connective tissue disorders		
Muscular weakness	-	20
Joint swelling	-	1
Myalgia	-	9
Osteonecrosis	-	2
Renal and Urinary disorders		
Renal insufficiency, renal failure, nephrotic syndrome	15	96
Reproductive system and breast disorders		
Vaginal hemorrhage, menorrhagia	-	3
General disorders and administration site conditions		
Fatigue, asthenia, malaise, health deterioration, performance status decreased	16	325
Pyrexia	1	190
Mucosal inflammation	1	53
Pain, chest pain	2	52
Edema, peripheral edema	-	17
Rigors, chills	-	12
Enanthema	-	1
Investigations		
Prothrombin time or INR prolonged	-	34
Liver function test (eg, transaminases, AP) abnormal/increased	-	114
Blood creatinine abnormal/increased	-	24
Blood bilirubin increased	-	26
Weight decreased	1	26
Blood urea increased	-	3
Ejection fraction decreased	-	2
Fecal occult blood positive	-	1
Hemoglobin decreased	-	20
Neutrophil count decreased	-	18
Amylase/Lipase increased	-	7
Injury, poisoning, and procedural complications		
Radiation pneumonitis	2	12

2.2 Rationale for Erlotinib in AML

Recently anecdotal reports have suggested that erlotinib can induce complete remission in patients with acute myeloid leukemia being treated for a concomitant non-small cell lung cancer.^{3,4} This was assumed to be an off target effect of erlotinib, but the exact mechanism was not clear. Previous reports had suggested that both gefitinib and erlotinib induced apoptosis in leukemic cell lines and cells obtained from patients with acute myeloid leukemia and myelodysplastic

syndromes, while sparing normal CD34+ cells.⁵⁻⁸ Gefitinib was also found to have a differentiation effect.⁸ Using proteomic and RNA1-based approaches Syk was identified as the off target for these agents in AML.⁹ This effect was confirmed using a somewhat specific Syk inhibitor, R406 which demonstrated that Syk inhibition can trigger differentiation of AML and MDS cells.⁹ A similar effect was observed with gefitinib.⁹ Importantly, Syk mRNA and protein is widely expressed in AML,¹⁰ during B-cell development¹¹, in myeloid and other hematopoietic cells¹², and in primary CLL lymphocytes¹³. Inhibition of Syk with fostamatinib has also demonstrated significant antileukemia activity in chronic lymphocytic leukemia^{14,15} and acute lymphoblastic leukemia¹⁶. We thus hypothesize that erlotinib may have significant clinical activity in patients with AML, possibly through inhibition of Syk.

3.0 STUDY DESIGN

- This will be a phase II, single-arm, open-label study.
- All patients will receive therapy with erlotinib administered orally as a continuous daily dose in 28-day cycles. Patients will continue therapy until clinically significant progression of the disease or unacceptable toxicity.
- The historical experience in this patient population is that response with standard therapy, when available, is less than 1%. In many instances (eg, patients with myelodysplastic syndrome failing hypomethylating agents), no standard therapy is even available. Thus, an overall response rate of 20% will be considered significant.

4.0 PATIENT SELECTION

Patients must have baseline evaluations performed prior to the first dose of study drug and must meet all inclusion and exclusion criteria. Results of all baseline evaluations, which assure that all inclusion and exclusion criteria have been satisfied, must be reviewed by the Principal Investigator or his/her designee prior to enrollment of that patient. In addition, the patient must be thoroughly informed about all aspects of the study, including the study visit schedule and required evaluations and all regulatory requirements for informed consent. The written informed consent must be obtained from the patient prior to initiating treatment. The following criteria apply to all patients enrolled onto the study unless otherwise specified.

4.1 Inclusion Criteria

4.1.1 Patients with AML who have either been refractory to prior therapy or have relapsed after prior therapy. Patients with MDS or CMML who received therapy with a hypomethylating agent and progress to AML are eligible if they have received any therapy for MDS and failed (i.e., lack or loss of response) regardless of whether they have received therapy for AML or not. The WHO classification will be used for AML.

- 4.1.2** Age \geq 18 years
- 4.1.3** ECOG Performance Status \leq 2
- 4.1.4** Adequate liver (total bilirubin \leq 2x ULN, ALT \leq 2.5x ULN) and renal (creatinine \leq 2x ULN) function.
- 4.1.5** Patients must provide written informed consent.
- 4.1.6** Patients must have been off chemotherapy for 2 weeks prior to entering this study, unless there is evidence of rapidly progressive disease, and must have recovered from the clinically significant toxic effects of that therapy to at least grade 1. Use of hydroxyurea for patients with rapidly proliferative disease is allowed before the start of study therapy and for the first four weeks on therapy.
- 4.1.7** Patients – both males and females – with reproductive potential (ie, menopausal for less than 1 year and not surgically sterilized) must practice effective contraceptive measures throughout the study. Women of childbearing potential must provide a negative pregnancy test (serum or urine) within 14 days prior to initiation of study.

4.2 Exclusion Criteria

- 4.2.1** Patients with known allergy or hypersensitivity to erlotinib.
- 4.2.2** Patients with any other known disease (except carcinoma in-situ) concurrent severe and/or uncontrolled medical condition (e.g. uncontrolled diabetes; cardiovascular disease including congestive heart failure NYHA Class III or IV, myocardial infarction within 6 months, and poorly controlled hypertension; chronic renal failure; or active uncontrolled infection) which, in the opinion of the investigator could compromise participation in the study.
- 4.2.3** Patients unwilling or unable to comply with the protocol.
- 4.2.4** Significant gastrointestinal disorders that may interfere with absorption of erlotinib.
- 4.2.5** Patients who can receive a stem cell transplant within 4 weeks.

5.0 TREATMENT PLAN

- 5.1 General:** All patients should be registered in CORe.

5.2 Treatment Plan: Patients will receive erlotinib therapy according to the suggested guidelines below. Individual minor variations in the initiation of therapy, are acceptable as indicated by patient condition and physician judgment. These variations should be documented in the patient's medical record.

5.2.1 Therapy: Patients will receive erlotinib at a dose of 150 mg orally, once daily in 28-day cycles.

5.2.2 Dose Adjustments: Dose adjustments will be done as described below using the following dose-levels:

Dose Level*	Erlotinib daily dose
0	150 mg
-1	100 mg
-2	50 mg

* Dose escalations/reductions different than those described in this table should be discussed with PI or Co-PI and documentation of the discussion made in the patient's medical record.

6.0 DOSE MODIFICATIONS AND MANAGEMENT OF TOXICITES

6.1 Dose Reduction Criteria for Hematologic Toxicity at Least Possibly Related to Erlotinib

Patients with AML usually present with abnormal peripheral blood counts at the time therapy is started and myelosuppression is an expected event during the course of therapy for acute leukemias. Thus, no dose adjustments or treatment interruptions for myelosuppression will be planned for the first 4 weeks of therapy unless an adjustment or interruption is considered by the investigator to be in the best interest of the patient. The reason for the variation should be documented in the patient's medical record. After this time, treatment interruptions and dose adjustments may be considered on an individual basis. The following guidelines can be used to consider treatment:

6.1.1 Patients with neutropenia or thrombocytopenia as a consequence of the disease do not require treatment interruptions for myelosuppression. Dose-reductions in these patients should be considered in an individual case and discussed with the PI. The following guidelines can be used for these patients:

6.1.1.1 Patients with a response and pre-cycle counts of neutrophils $>1 \times 10^9/L$ and platelets $>50 \times 10^9/L$ who have sustained low counts of neutrophils $<0.5 \times 10^9/L$ or a platelet count $<20 \times 10^9/L$ (eg, for more than 5 consecutive days) may have treatment interrupted. Upon recovery of counts to neutrophils $>1 \times 10^9/L$ and platelets to $>50 \times 10^9/L$ treatment may be re-started with a 1 dose level reduction. A reduction of 2 dose levels may

be considered if the myelosuppression was deemed severe and life threatening by the treating physician, and if it is in the patient's best interest.

6.1.1.2 If there are persistent peripheral blood blasts, or the bone marrow shows $>5\%$ blasts, may continue treatment regardless of neutrophil and platelet count and give supportive care as needed.

6.1.1.3 If no marrow evidence of leukemia, may hold therapy until recovery of granulocytes to $\geq 1 \times 10^9/L$ and platelets $\geq 50 \times 10^9/L$, then resume at same or 1 lower dose level according to guidelines mentioned above.

6.2 Dose Reduction Criteria for Non-Hematologic Toxicity at Least Possibly Related to Erlotinib

Toxicity (NCI CTCAE v4.0)	Dose Modification^a
Diarrhea	
Grade 1 or 2	None. May initiate therapy with loperamide or alternate antidiarrheal. See Section 6.3 for treatment details.
Grade 3 ^b or 4 ^b	^{a)} Interrupt erlotinib until resolution to \leq grade 2 and then restart 1 dose level lower. If the event does not resolve to \leq grade 2 within 14 days, erlotinib will be discontinued.
Rash	
Grade 1	None
Grade 2	None. Initiate treatment as outlined in Section 6.3. If rash persists and is intolerable or worsens over 10 – 14 days, then reduce by 1 dose level.
Grade 3 ^b	Reduce by 1 dose level. If rash persists or worsens over 10 – 14 days, then interrupt erlotinib until resolution to \leq grade 2 and then restart 1 dose level lower. If the event does not resolve to \leq grade 2 within 14 days, erlotinib will be discontinued.
Grade 4	Permanently discontinue erlotinib.
Interstitial Lung Disease (ILD)	
Any Grade	If ILD possibly related to study drug is suspected, erlotinib should be interrupted immediately pending diagnostic evaluation. If ILD is diagnosed, erlotinib should be discontinued permanently and appropriate treatment instituted as necessary.
Other Non-Hematologic Toxicities	
Grade 1 or 2	None
Grade 3 ^{b, c}	Interrupt erlotinib until resolution to \leq grade 2 and then restart 1 dose level lower.
Grade 4	Permanently discontinue erlotinib

a) Doses that have been reduced 1 dose level for toxicity may be re-escalated to the previous

dose level only if the toxicity abates or returns to baseline severity and the investigator believes it is in the best interest of the patient. Doses that have been reduced 2 dose levels for toxicity may only be re-escalated to the previous dose level (ie, dose level at first reduction) and only if the toxicity abates or returns to baseline severity and the investigator believes it is in the best interest of the patient. Doses that have been reduced 2 or more dose levels for toxicity may not be re-escalated to the starting dose level (or dose-escalated dose for tobacco smokers). Any patient who fails to tolerate treatment at 50 mg/day will be discontinued from the study.

- b) If not responding to optimal treatment within 48 hrs.
- c) Only if ≥ 2 grade level change from baseline

6.3 Suggested Management of Toxicity: The following guidelines are offered as suggestions for the management of toxicity. Variations of these are acceptable based on the patient's individual circumstances and physician preference.

If a patient experiences several toxicities, dose adjustments are to be made based on the greatest degree of toxicity (ie, reducing the dose to the lowest level). If significant toxicity is still apparent, the dose may be reduced a second time. Any patient who fails to tolerate treatment of 50 mg/day will be withdrawn from the study.

Antidiarrheal and antirash medications may be introduced at any time if clinically indicated. Previous phase 1 and 2 studies have demonstrated that the frequency and severity of diarrhea can be managed with loperamide. The recommended dose of loperamide is 4 mg at first onset, followed by 2 mg every 2 to 4 hours until diarrhea resolves for 12 hours. Other antidiarrheal medications may be used as clinically indicated.

In the event of severe or persistent diarrhea, nausea, anorexia, or vomiting associated with dehydration due to erlotinib therapy, erlotinib should be interrupted and appropriate measures should be taken to intensively treat the dehydration.

Patients may be informed that skin toxicity is to be expected during treatment with erlotinib. Skin toxicity may take the form of dry skin, rash, acneiform eruption, or hair or nail changes. Prophylactic treatment of the skin may prevent or reduce skin toxicity. The patient should be encouraged to use an alcohol-free, emollient cream applied twice a day to the entire body as soon as the patient starts therapy with erlotinib. Creams and ointments are recommended because they have a greater ability to retain moisture than lotions. Examples of suitable emollient creams include: Neutrogena® Norwegian formula, SARNA® Ultra, Vanicream™, Aveeno® (fragrance-free formulation), and Eucerin® cream. Other over-the-counter aqueous creams or emulsifying ointments may also provide symptomatic benefit. Lotions are not recommended because they often contain alcohol, which may dry the skin. Patients may also be encouraged to use a titanium dioxide or zinc oxide-based sunscreen product applied to sun-exposed areas twice per day.

Patients who develop skin toxicity and are symptomatic may be treated with topical therapy such as hydrocortisone cream or clindamycin gel. If needed, oral minocycline or oral doxycycline may be combined with the topical therapy. A topical immodulating cream such as Elidel could also be considered. For more severe rash, oral corticosteroids may be beneficial. Patients who fail to respond to these measures may have the dose of erlotinib interrupted or reduced. See Annex 5 for more information on skin toxicity management.

Minocycline may interfere with anticoagulants and oral contraceptives. Patients treated with minocycline who are taking anticoagulants and/or oral contraceptives should be monitored accordingly.

There have been infrequent reports of serious ILD, including fatal events, in patients receiving erlotinib for the treatment of NSCLC and other advanced solid tumors. In the event of acute onset of new or progressive, unexplained pulmonary symptoms such as dyspnea, cough, and fever, where ILD is suspected, study drug should be interrupted pending diagnostic evaluation. If ILD is diagnosed, study drug should be permanently discontinued and appropriate treatment instituted as necessary.

Treatment with erlotinib should be used with extra caution in patients with total bilirubin $> 3 \times$ ULN. Patients with hepatic impairment (total bilirubin $>$ ULN or Child-Pugh A, B and C) should be closely monitored during therapy with erlotinib.

Gastrointestinal perforation (including fatalities) has been reported in patients receiving erlotinib. Patients receiving concomitant anti-angiogenic agents, corticosteroids, NSAIDs, and/or taxane-based chemotherapy, or who have prior history of peptic ulceration or diverticular disease are at increased risk. Permanently discontinue erlotinib in patients who develop gastrointestinal perforation.

Bullous, blistering and exfoliative skin conditions have been reported, including cases suggestive of Stevens-Johnson syndrome/toxic epidermal necrolysis, which in some cases were fatal. Interrupt or discontinue erlotinib treatment if the patient develops severe bullous, blistering, or exfoliating conditions.

Ocular Disorders, including corneal perforation or ulceration have been reported during use of erlotinib. Other ocular disorders including abnormal eyelash growth, keratoconjunctivitis sicca or keratitis have been observed with erlotinib treatment and are known risk factors for corneal ulceration/perforation. Interrupt or discontinue erlotinib therapy if patients present with acute/worsening ocular disorders such as unexplained eye pain.

Erlotinib dosing should be discontinued for any severe toxicity that does not respond to treatment or failure to recover within 14 days from hematological toxicity attributable to erlotinib.

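### Section 6.2 applies the 48-hour wait to grade 4 diarrhea, so an event that responds in that time triggers no hold or dose reduction in the table

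*Combined protocol and SAP*

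**What the plan says.** The section 6.2 table covers non-hematologic toxicity at least possibly related to erlotinib, graded by CTCAE v4.0. Its diarrhea row handles grades 3 and 4 together and prints footnote mark b on each number separately. The action is to interrupt until grade 2 or less and restart one dose level lower, with a time limit: if the event has not come down to "grade 2 within 14 days, erlotinib will be discontinued". Footnote b makes that action conditional: "If not responding to optimal treatment within 48 hrs".

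At grade 4, the rash row and the Other row both say "Permanently discontinue erlotinib", without footnote b. For suspected interstitial lung disease (ILD) of any grade, "erlotinib should be interrupted immediately pending diagnostic evaluation".

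Footnote a governs what follows a reduction. "Doses that have been reduced 1 dose level for toxicity may be re-escalated to the previous" level if the toxicity abates and the investigator judges it best for the patient. At the bottom of the range, "Any patient who fails to tolerate treatment at 50 mg/day will be discontinued from the study".

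Section 6.3 adds: "In the event of severe or persistent diarrhea, nausea, anorexia, or vomiting associated with dehydration due to erlotinib therapy, erlotinib should be interrupted". It opens, however, with "The following guidelines are offered as suggestions for the management of toxicity", and accepts variation by circumstances and physician preference. It also says that loperamide can manage the frequency and severity of diarrhea. Section 6.4 bars escalation to a dose level at which the patient had grade 4 toxicity.

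**The concern.** A grade 4 event attributed to the study drug would normally prompt a hold while it is treated. Here the table's only action at grade 4 diarrhea depends on 48 hours of non-response, and no alternative is given for a patient who does respond. Read literally, that patient can keep taking the full daily dose during the event and stay on the same dose afterwards.

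Footnote b also asks for response, not resolution. Improvement from grade 4 to grade 3 could count as response, so dosing could continue past 48 hours with the event still above the grade 2 level that the same row requires for a restart.

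What is at stake is the safety of individual patients. The serious related events tabulated in section 2.1.1 show that diarrhea is not a minor toxicity of this drug: it has the largest total of any row.

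**Working it through.** There is no plan figure to reproduce. The check sets the table's rows side by side and works out the dose consequences.

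**Rows of 6.2 that cover grade 4**

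| Row | Names grade 4? | Footnote b at grade 4? | Action |
|---|---|---|---|
| Diarrhea | Yes | Yes | Interrupt, restart one level lower, only after 48 h of non-response |
| Rash | Yes | No | Permanent stop |
| Other | Yes | No | Permanent stop |
| ILD | No (any grade) | No | Interrupt on suspicion |

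Three rows name grade 4 and one of them carries the wait. In the rash and Other rows, b is on grade 3 and absent at grade 4. ILD is a weaker comparator, because suspicion of a diagnosis triggers it, not grade.

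**Who is left uncovered**

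- Non-responders at 48 hours: covered by the diarrhea row.
- Severe or persistent diarrhea with dehydration: 6.3 suggests interruption without a wait, but specifies no dose reduction.
- Grade 4 dehydration as an event in its own right: a permanent stop under Other.
- Grade 4 diarrhea, no recognised dehydration, response within 48 hours: no hold or reduction in 6.2, and no hold advised for it in 6.3.

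**Dose consequences** (dose levels 150, 100 and 50 mg/day, section 5.2.2)

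- Doses inside the wait: 48 h / 24 h = 2. At 150 mg, 2 × 150 = 300 mg. At 100 mg, 2 × 100 = 200 mg.
- As written, a responder at 150 mg stays there: 28 × 150 = 4,200 mg per full cycle.
- With an immediate hold and restart at 100 mg: 28 × 100 = 2,800 mg per full cycle, which is 1,400 mg less, and (150 − 100)/150 = 33% lower.
- From 100 mg the restart is at 50 mg: (100 − 50)/100 = 50% lower.

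These figures measure exposure, not harm avoided.

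**Context from section 2.1.1** (counts of serious related events, not rates)

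- Diarrhea: 873 events, 16 fatal.
- Main rash row: 698 events, none fatal.
- Vomiting: 332 events, 2 fatal.

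Grade 4 rash is a permanent stop, and so is grade 4 vomiting under Other. Diarrhea, the largest row, has the most lenient grade 4 rule.

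**Fit with 6.4.** A patient reduced after grade 4 toxicity at 150 mg may not go back to 150 mg. A patient whose grade 4 diarrhea at 150 mg responds within 48 hours need not leave it.

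**The case against.** The strongest reply is that the exception is deliberate. Mark b is printed on both numbers, the whole row is gentler than the others because it allows a restart, and 6.3 supplies a reason, namely that loperamide works. Making action depend on response to treatment is also used elsewhere: b is on grade 3 rash and grade 3 Other, and 6.3 discontinues dosing for severe toxicity that does not respond to treatment. The affected group is narrow, has no rate in the documents, and may be empty among 29 patients.

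Much of this stands. The wait may well be intended, and I do not call it a slip. But the loperamide argument supports bringing the drug back after grade 4 diarrhea, which the fix preserves. It does not by itself support dosing during the event.

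Four stronger readings are tempting, and the documents do not support them:

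- **The plan requires dosing to continue through grade 4 diarrhea.** It does not. Nothing forbids a hold, section 5.2 calls the treatment plan suggested guidelines, and section 3.0 ends therapy for unacceptable toxicity.
- **Patients with dehydration are unprotected.** Section 6.3 advises interruption for them, though only as a suggestion.
- **Three comparable grade 4 rules contradict this one.** Only rash and Other name grade 4.
- **Trial-level safety monitoring is weakened.** The toxicity definition in 11.1 counts clinically significant, possibly related non-hematologic grade 3 or 4 events and has no 48-hour condition.

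**Conclusion.** The point holds for a limited group: grade 4 erlotinib-related diarrhea, without recognised dehydration, that responds within 48 hours. For these patients neither 6.2 nor 6.3 calls for a hold, and the table calls for no reduction. At the starting dose the exposure at issue is two doses (300 mg) inside the wait, possibly more if response falls short of resolution, followed by 150 mg/day where a restart would be at 100 mg/day.

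This rests on the printed footnote marks being as intended and on reading footnote b literally. No number of affected patients can be given. It is worth considering as a low-cost safety improvement even if the exception was deliberate. It is not a flaw in the efficacy design.

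A reader might infer that the change cannot touch ORR. That is true of the endpoint definition, the sample size and the stopping boundaries. It is not assured for observed responses: affected patients would receive less drug, the documents give no dose-response data in AML, and two responses among 29 patients decide the result.

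**What to change.** In the 6.2 diarrhea row, remove footnote mark b from the 4 and keep it on the 3. Grade 4 diarrhea is then interrupted at once and restarted one level lower after resolution to grade 2 or less. The 14-day limit is unchanged.

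I would not also write the 6.3 dehydration advice into footnote b. Section 6.3 already advises that hold. Moving it into the table would attach a mandatory reduction that 6.3 does not specify, and would leave unclear whether footnote c (a change of at least two grades from baseline) still applies to grade 3 events in the Other row.

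The cost is a one-mark wording amendment with no added procedures. A patient whose diarrhea would have settled within 48 hours misses some doses and steps down, for example from 150 to 100 mg. Footnote a allows re-escalation in general, but 6.4 bars return to a level where grade 4 toxicity occurred, so the step is probably lasting. A patient already at 50 mg/day has no lower level and would be discontinued under footnote a.
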